11.1.1 Other significant adverse events (OAE)

During the evaluation of the AE data, an AstraZeneca medically qualified expert will review the list of AEs that were not reported as SAEs and discontinuation of Investigational Product due to Adverse Events (DAEs). Based on the expert's judgement, significant adverse events of particular clinical importance may, after consultation with the Global Patient Safety Physician, be considered OAEs and reported as such in the Clinical Study Report. A similar review of laboratory and/vital signs data will be performed for identification of OAEs.

Examples of these are marked haematological and other laboratory abnormalities, and certain events that lead to intervention (other than those already classified as serious), dose reduction or significant additional treatment.

11.2 Calculation or derivation of pharmacokinetic variables

The pharmacokinetic (PK) analyses of the plasma concentration data for dapagliflozin and metformin will be performed by Derivation of PK parameters will be performed

using the WinNonlin's standard non-compartmental approach (WinNonLin version 5.01, WinNonLin, Pharsight, Mountain View, CA, USA).

The actual sampling times will be used in the PK parameter calculations. Plasma concentrations below limit of quantification (LOQ) will be excluded from the calculations except at time points prior to C_{max} , where plasma concentrations below LOQ will be taken as zero at protocol time zero and as missing at all other time points in the calculation.

The primary objectives of the study are to determine AUC_{0-t} , AUC_{inf} and C_{max} for dapagliflozin and metformin as single doses and within each FDC formulation and the and bioequivalence will be tested with respect to these two PK parameters for

Part I: one 2.5 mg/850 mg FDC tablet and one single dose of 2.5 mg dapagliflozin together with one single dose of 850 mg metformin

and

Part II: one 5 mg/1000 mg FDC tablet and one single dose of 5 mg dapagliflozin together with one single dose of 1000 mg metformin

all administered in the fed state.

The following PK parameters will be determined:

- $AUC_{(0-t)}$ Area under plasma concentration-time curve from zero to time t [amount•time/volume]
- AUC_{inf} Area under plasma concentration-time curve from zero to infinity [amount•time/volume]
- C_{max} Maximum plasma (peak) drug concentration [amount/volume]
- t_{max} The time relative to administration to reach C_{max} , [h]
- $t_{1/2}$ The terminal phase half-life calculated as $\ln(2)/\lambda_z$, [h^{-1}]

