3. STUDY PLAN AND PROCEDURES

This Clinical Study Protocol has been subject to a peer review according to AstraZeneca standard procedures.

This study is a single-centre, two parts, randomized, open label, crossover bioequivalence study. The first part is a two-way crossover comparing the newly formulated FDC dapagliflozin/metformin IR (2.5 mg/850 mg) tablet to the individual dapagliflozin and metformin IR tablets administered together. The second part is a two-way crossover comparing the newly formulated FDC dapagliflozin/metformin IR (5 mg/1000 mg) tablet to the individual dapagliflozin and metformin IR tablets administered together. See also [Figure 1](#) and [Figure 2](#). Parts I and II are independent of each other, and may be carried out simultaneously.

[figure not shown]
A total of 120 male and non-fertile female healthy volunteers will be included in this study with 60 in each study part. Healthy volunteers participating in Part I will not be enrolled in Part II. Healthy volunteers participating in Part II will not be enrolled in Part I.

All treatments will be administered to the healthy volunteers in the fed state.

In Part I, healthy volunteers will be randomized to one of two sequences in a 1:1 allocation. Sequence 1 will administer the FDC in period 1 and the free combination in period 2. Sequence 2 will administer the treatments in the reverse order. For Part II, healthy volunteers will be randomized in the same way as in Part I.

[figure not shown]
An enrolment examination for eligibility will be performed within 19 days before the dosing. Randomization will take place immediately before the first dosing. The wash-out period between both dosing periods will be at least 7 days. Following last dosing, a follow-up examination will be performed at least 6 days after the last PK sample 72 hours post-dose has been taken. The overall duration for each subject will be approximately 38 days.

Figure 1 Part I (2.5 mg + 850 mg)

FDC=Fixed dose combination, PK=pharmacokinetic, Dapa = Dapagliflozin

Figure 2 Part II (5 mg + 1000 mg)

FDC=Fixed dose combination, PK=pharmacokinetic, Dapa = Dapagliflozin

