12.2.3 Pharmacokinetics

The primary objectives of this study are to demonstrate bioequivalence for newly formulated FDC tablets versus the individual dapagliflozin and metformin IR tablets (free combination) of dapagliflozin/metformin 2.5 mg/850 mg and for 5 mg/1000 mg. For both objectives, bioequivalence will be demonstrated if the 90% confidence interval (CI) for the formulation effect is contained within the interval of 0.8000-1.2500 for $AUC_{(0-t)}$, AUC_{inf} and C_{max} with respect to both dapagliflozin and metformin.

The study has two parts: Part I is 2-treatment, 2-period, crossover design to evaluate bioequivalence for the 2.5 mg/850 mg formulation and Part II is a 2-treatment, 2-period, crossover design to evaluate bioequivalence for the 5 mg/1000 mg formulation. In Part I, subjects will be randomized to one of two sequences in a 1:1 allocation. Sequence 1 will administer the FDC in period 1 and the free combination in period 2. Sequence 2 will administer the treatments in the reverse order. For Part II, subjects will be randomized in the same way as in Part I.

$AUC_{(0-t)}$, AUC_{inf} and C_{max} will be log-transformed prior to analysis. All endpoints will be analyzed using an analysis of variance (ANOVA) model for each part separately, with sequence, period and formulation as fixed effects and subject within sequence as a random effect. The results of the analysis will be presented in terms of the estimated geometric mean for each formulation with corresponding 95% confidence interval, and the estimated

formulation effect (ratio of geometric means) with a 90% confidence interval. Geometric means will be estimated by back-transformation of least squares means from the log-transformed data with adjustment for any imbalances in the design. All other pharmacokinetic parameters will be summarized by formulation using descriptive statistics only.

Graphical presentations will be used as appropriate. Examples may include line graphs showing individual or mean development over time.

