12.3 Determination of sample size

To determine the sample size for this study, initial estimates of formulation effect (geometric mean ratio) were obtained from Bristol-Myers Squibb Study MB102026 which examined a different FDC of dapagliflozin and metformin. Estimates of the intra-subject variability (MSE) for dapagliflozin $AUC_{(0-t)}$ and metformin C_{max} and $AUC_{(0-t)}$ were also obtained from this study, whereas the estimate for dapagliflozin C_{max} was obtained from Bristol-Myers Squibb Study MB102005 (the median estimate from dapagliflozin studies MB102005, MB102019 and MB102026). From these sources, data for initial estimates of formulation

effect and assumed intra-subject variability (MSE of log-transformed data) were 0.932 (0.041), 1.005 (0.009), 0.953 (0.025), and 1.001 (0.012), for dapagliflozin C_{\max} and $AUC_{(0-t)}$, and metformin C_{\max} and $AUC_{(0-t)}$, respectively.

If the ratio of true geometric means is actually 0.90 for dapagliflozin C_{\max} , 1.00 for dapagliflozin $AUC_{(0-t)}$, 0.95 for metformin C_{\max} , and 1.00 for metformin $AUC_{(0-t)}$, then with 54 evaluable subjects in Part I, there is 90% power to establish bioequivalence with respect to dapagliflozin C_{\max} and >99% power for each of the remaining 5 measures (assuming same results for AUC_{inf} as for $AUC_{(0-t)}$). With 6 subjects anticipated not to complete both periods of the study, a total of 60 subjects are needed in each Part.

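### Dropping post-dose, pre-peak values below LOQ overstates AUC when a delay leaves early samples unquantifiable; the effect on the bioequivalence ratio is small

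*Protocol*

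**What the plan says.** Protocol section 11.2 derives the parameters by WinNonlin's "standard non-compartmental approach" and adds that "The actual sampling times will be used in the PK parameter calculations". Concentrations below LOQ "will be excluded from the calculations except at time points prior to" Cmax. Before Cmax they are "taken as zero at protocol time zero and as missing at all other time points in the calculation". The pre-dose sample therefore becomes zero, while an unquantifiable sample at 0:15, 0:30, 1:00 or any later time before the peak is dropped. No other section changes this.

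The rule feeds two of the three variables that decide each part. Section 12.2.3 applies one criterion to AUC(0-t), AUCinf and Cmax of each analyte: "bioequivalence will be demonstrated if the 90% confidence interval (CI) for the formulation effect is contained within the interval of 0.8000-1.2500". Table 2 places the first post-dose samples at 0:15, 0:30, 1:00, 1:30 and 2:00. Section 3 states: "All treatments will be administered to the healthy volunteers in the fed state".

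**The concern.** A sample below LOQ still carries information: the concentration at that time was under the assay limit. Deleting it lets the trapezoid draw a straight line across the interval, so the profile is credited with exposure where the assay found none that it could quantify. This is a stated calculation rule, not a detail left open.

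Early unquantifiable samples are plausible here, because tablets are taken after a meal and sampling starts at 15 minutes. The comparison is one combined tablet against two separate ones, and a difference in release lag is one way these could differ. The product that lags longer gains area, so the FDC/free ratio would rise if the FDC lags and fall if the free combination does. Lag that varies between a volunteer's two periods would also add some within-subject noise.

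**Working it through.** **The plan's own figures.** Section 12.3 gives formulation effects with MSEs that "were 0.932 (0.041), 1.005 (0.009), 0.953 (0.025), and 1.001 (0.012), for dapagliflozin" Cmax and AUC(0-t) and metformin Cmax and AUC(0-t), in that order. It assumes 54 evaluable subjects. Using two one-sided t-tests at 5%, SE = √(2 × MSE/54), 52 degrees of freedom and limits 0.80–1.25:

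- Dapagliflozin Cmax at a true ratio of 0.90 and MSE 0.041: power 0.910 (stated 90%).
- Dapagliflozin AUC, metformin Cmax and metformin AUC at their assumed ratios: power above 0.999 (stated >99%).
- Sample size: 54 + 6 = 60, as stated.

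**Excess in one profile.** Let t(k−1) be the last pre-peak time below LOQ and C(k) the first quantifiable value, at t(k).

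- Rule in 11.2: area to t(k) = 0.5 × t(k) × C(k).
- Zero substitution: area to t(k) = 0.5 × (t(k) − t(k−1)) × C(k).
- Excess = 0.5 × t(k−1) × C(k), which is always positive.

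Example: 0:15 and 0:30 below LOQ, 1:00 quantifiable at c. The rule gives 0.5 × 1 × c = 0.50c and zero substitution gives 0.5 × (1 − 0.5) × c = 0.25c, so the excess is 0.25c. Choosing a linear or a log-down trapezoid does not matter, because this segment rises from zero. AUCinf carries the same added area. Cmax and tmax do not change. If the lag is under 0.25 h, the 0:15 sample is normally quantifiable and the excess is zero.

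**Size per profile.** The protocol gives no lag, LOQ or half-life. Assumed: one-compartment oral profile, half-life 5–8 h, ka 1–2 per hour, LOQ at 1% of Cmax, Table 2 nominal times, linear trapezoid.

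| Lag | Excess in AUC(0-t) over zero substitution |
|---|---|
| 0.3–0.8 h | about 0.2–2% |
| 1.05–1.3 h | about 0.8–4% |

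The ends of the first range move to about 0.1% and 2.1% with the spacing of the lags tried. Over a much wider set (half-life 3–13 h, ka 0.5–4 per hour) the range is 0.06–9.3%.

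**Which convention is nearer the truth.** With equal true AUC, a lag on one product only, and another assumed set (ka 0.7–3 per hour at half-life 4 h, ka 1.5 per hour at 12 h, LOQ 0.5% of Cmax), the one-profile AUC ratio should be 1.00:

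| Lag | Rule in 11.2 |
|---|---|
| 0.3 h | 1.002–1.010 |
| 0.55 h | 1.007–1.030 |
| 1.1 h | 1.013–1.062 |

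With zero substitution the ratio stays within 0.9997–1.004 throughout.

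**Shift in the study ratio.** On the log scale the shift is the mean of the subjects' log excesses. If 20% of subjects lag 1.05–1.3 h on one product only:

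- Upper end: exp(0.2 × ln 1.04) − 1 = exp(0.00784) − 1 ≈ 0.79%.
- Lower end: exp(0.2 × ln 1.008) − 1 ≈ 0.16%.

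With lags of 0.3–0.8 h in 20% of subjects, the upper end is exp(0.2 × ln 1.021) − 1 ≈ 0.42%.

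**Against the precision of the ratio.** The 90% CI half-width is exp(t(0.95, 52) × SE) − 1, with t = 1.6747.

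- MSE 0.009: SE = √(0.018/54) = 0.01826, half-width 3.1%.
- MSE 0.012: SE = √(0.024/54) = 0.02108, half-width 3.6%.

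The largest observed AUC ratio that still passes is 1.25/1.031 ≈ 1.21. If every subject carried the extreme 9.3% on one product at a true ratio of 1.00, the upper limit would be 1.093 × 1.036 ≈ 1.13. AUC power stays above 99.9% even at a true ratio of 1.10.

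**The case against.** The strongest reply is that nothing in the protocol shows the two products lagging differently. All are immediate-release tablets, taken after the same standardised meal with identical menus at both dosing visits (section 5.1). With similar lags the excess largely cancels in the within-subject ratio. The AUC ratios from the earlier study of a different FDC were 1.005 and 1.001 (section 12.3). Below LOQ also does not mean zero: missing and zero are both conventions, and this one is prespecified and common to both products and analytes.

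Most of this stands, and it limits the size of the point. It does not remove it. The rule overstates AUC in any profile with an unquantifiable post-dose sample before the peak, and zero substitution is clearly nearer the true ratio in the assumed cases with unequal lags.

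Two stronger readings are tempting, and neither is supported. A reader might infer that any delay in absorption inflates AUC, but a lag shorter than the first sampling time leaves nothing to drop. A reader might also set the 0.8–4% excess beside the 3.1–3.6% half-width and infer that the point estimate could move by about its own interval. Those are unlike quantities: the first belongs to one profile, the second to a mean ratio over 54 subjects. They become comparable only if nearly every subject lags more than an hour on one product and on the other has no lag long enough to leave a sample below LOQ. The documents give no ground for assuming that.

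**Conclusion.** The point holds as a minor one. Section 11.2 fixes a rule that biases AUC(0-t) and AUCinf upward, relative to zero substitution, in every profile with at least one unquantifiable post-dose sample before the peak. The direction follows from the geometry and needs no assumption about the drugs. The size does: about 0.2–2% of a profile's AUC for lags of 0.3–0.8 h and about 0.8–4% for lags of 1.05–1.3 h, under the one-compartment assumptions stated.

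The formulation ratio is biased only if lags differ between products. The shift is under about 0.8% if 20% of subjects lag on one product only. A changed verdict is very unlikely: AUC would have to lie close to a limit already, whereas section 12.3 plans on true AUC ratios of 1.00. Cmax, which drives the sample size, is untouched.

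**What to change.** Replace the pre-peak rule in section 11.2 with: *Concentrations below LOQ at pre-dose and at all times before the first quantifiable concentration are set to zero; those after the first quantifiable concentration are excluded.* Apply it identically to both formulations and both analytes. Naming the pre-dose sample keeps the explicit zero at time zero that the present text provides.

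The cost is one sentence and one setting in the non-compartmental analysis, with no new samples or data. It should be settled before concentrations are seen, because the direction of any bias in the ratio depends on which product lags. The drawback is a possible departure from a sponsor standard rule. In that case keep the present rule for the primary analysis and prespecify zero substitution as a sensitivity analysis for AUC(0-t) and AUCinf.

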12. STATISTICAL METHODS AND SAMPLE SIZE DETERMINATION BY ASTRAZENECA OR DELEGATE

12.1 Description of analysis sets

12.1.1 Pharmacokinetic analysis set

The PK analysis will be performed using the PK analysis set including all subjects who received the investigational product and who have evaluable PK data appropriate for the

comparison of interest (with no major protocol deviations or violations thought to significantly affect the pharmacokinetics of the drug).

12.1.2 Safety analysis set

The safety population is defined as all subjects who receive at least one dose of IP and for whom any post-dose data are available. The safety population will be used for the analysis of all safety variables and the analysis will be done according to actual treatment received, regardless of randomisation. Post-dose data imply that there was a contact during which an opportunity was given to report any health problems.

12.2 Methods of statistical analyses

12.2.1 General principles

The PK analysis will be performed using the PK analysis set including all subjects who received the investigational product and who have evaluable PK data appropriate for the comparison of interest (with no major protocol deviations or violations thought to significantly affect the pharmacokinetics of the drug).

12.2.2 Subject characteristics

Continuous variables will be summarised using descriptive statistics (n, mean, standard deviation [SD], min, median, max). Categorical variables will be summarised in frequency tables (frequency and proportion) by treatment.

12.2.3 Pharmacokinetics

The primary objectives of this study are to demonstrate bioequivalence for newly formulated FDC tablets versus the individual dapagliflozin and metformin IR tablets (free combination) of dapagliflozin/metformin 2.5 mg/850 mg and for 5 mg/1000 mg. For both objectives, bioequivalence will be demonstrated if the 90% confidence interval (CI) for the formulation effect is contained within the interval of 0.8000-1.2500 for $AUC_{(0-t)}$, AUC_{inf} and C_{max} with respect to both dapagliflozin and metformin.

The study has two parts: Part I is 2-treatment, 2-period, crossover design to evaluate bioequivalence for the 2.5 mg/850 mg formulation and Part II is a 2-treatment, 2-period, crossover design to evaluate bioequivalence for the 5 mg/1000 mg formulation. In Part I, subjects will be randomized to one of two sequences in a 1:1 allocation. Sequence 1 will administer the FDC in period 1 and the free combination in period 2. Sequence 2 will administer the treatments in the reverse order. For Part II, subjects will be randomized in the same way as in Part I.

$AUC_{(0-t)}$, AUC_{inf} and C_{max} will be log-transformed prior to analysis. All endpoints will be analyzed using an analysis of variance (ANOVA) model for each part separately, with sequence, period and formulation as fixed effects and subject within sequence as a random effect. The results of the analysis will be presented in terms of the estimated geometric mean for each formulation with corresponding 95% confidence interval, and the estimated

formulation effect (ratio of geometric means) with a 90% confidence interval. Geometric means will be estimated by back-transformation of least squares means from the log-transformed data with adjustment for any imbalances in the design. All other pharmacokinetic parameters will be summarized by formulation using descriptive statistics only.

Graphical presentations will be used as appropriate. Examples may include line graphs showing individual or mean development over time.

12.2.4 Safety and tolerability

Continuous variables will be summarised using descriptive statistics (n, mean, SD, min, median, max) by treatment group. Categorical variables will be summarised in frequency tables (frequency and proportion) by treatment group. Graphical presentations will be used as appropriate. Examples include shift plots showing pre-treatment values on the horizontal axis and post-treatment values on the vertical axis.

12.2.4.1 Adverse events

Adverse events will be summarised by preferred term and system organ class using MedDRA vocabulary. Furthermore, listings of serious adverse events and adverse events that led to withdrawal will be made and the number of subjects who had any AEs, SAEs, AEs that led to withdrawal, and adverse events with severe intensity will be summarised. AEs that occur before dosing will be reported separately.

12.2.4.2 ECG

ECG results will be summarized in a frequency table displaying number of subjects with a normal/abnormal assessment. Individual subject data will be provided in a listing.

12.2.4.3 Laboratory variables

Clinical chemistry, haematology and urinalysis variables will be described by shift plots, descriptive statistics, subject listings and frequency tables of values outside project specific reference ranges, details of which will be presented in a separate comprehensive SAP.

12.2.4.4 Vital Signs

Summary statistics for all vital signs data will be presented and will include mean, standard deviation, min, max, details of which will be presented in a separate comprehensive SAP.

12.3 Determination of sample size

To determine the sample size for this study, initial estimates of formulation effect (geometric mean ratio) were obtained from Bristol-Myers Squibb Study MB102026 which examined a different FDC of dapagliflozin and metformin. Estimates of the intra-subject variability (MSE) for dapagliflozin $AUC_{(0-t)}$ and metformin C_{max} and $AUC_{(0-t)}$ were also obtained from this study, whereas the estimate for dapagliflozin C_{max} was obtained from Bristol-Myers Squibb Study MB102005 (the median estimate from dapagliflozin studies MB102005, MB102019 and MB102026). From these sources, data for initial estimates of formulation

effect and assumed intra-subject variability (MSE of log-transformed data) were 0.932 (0.041), 1.005 (0.009), 0.953 (0.025), and 1.001 (0.012), for dapagliflozin C_{\max} and $AUC_{(0-t)}$, and metformin C_{\max} and $AUC_{(0-t)}$, respectively.

If the ratio of true geometric means is actually 0.90 for dapagliflozin C_{\max} , 1.00 for dapagliflozin $AUC_{(0-t)}$, 0.95 for metformin C_{\max} , and 1.00 for metformin $AUC_{(0-t)}$, then with 54 evaluable subjects in Part I, there is 90% power to establish bioequivalence with respect to dapagliflozin C_{\max} and >99% power for each of the remaining 5 measures (assuming same results for AUC_{inf} as for $AUC_{(0-t)}$). With 6 subjects anticipated not to complete both periods of the study, a total of 60 subjects are needed in each Part.

13.2 Overdose

An overdose is defined as the accidental or intentional ingestion of any dose of a product that is considered both excessive and medically important. **All occurrences of overdose must be reported as an SAE (see section 6.3.2).** If an overdose is suspected, monitoring of vital functions as well as treatment as appropriate should be performed.

13.3 Pregnancy

If a patient becomes pregnant, the investigational product should be stopped and the study monitor should be informed. The pregnancy report module in the CRF should be completed by the investigator and the study monitor will forward the information to Bristol-Myers Squibb using the same procedure as for SAE reporting (6.3.2). The outcome of each pregnancy will also be collected once this information is available.

Pregnancy itself is not regarded as an AE unless there is a suspicion that the investigational product under study may have interfered with the effectiveness of a contraceptive medication.

However, the outcome of all pregnancies (spontaneous miscarriage, elective termination, normal birth or congenital abnormality) must be followed up and documented even if the patient was discontinued from the study.

All reports of congenital abnormalities/birth defects are SAEs. Spontaneous miscarriages should also be reported and handled as SAEs. Elective abortions without complications should not be handled as AEs.

